## PROTOCOL SYNOPSIS

Title	The ViDMe Project "Vitamin D supplementation in cutaneous malignant melanoma outcome"
EudraCT No.	2012-002125-30
Phase	III
Sponsor	UZ Leuven
Coordinating Investigator	[name]
Study Objectives	To assess whether vitamin D supplementation, in the follow up period after diagnosis and surgery of the primary tumor, has a protective effect on relapse of cutaneous malignant melanoma and whether this protective effect correlates with vitamin D levels in serum and vitamin D receptor (VDR) immunoreactivity in the primary tumor.
Design	double-blind randomized placebo-controlled study
Treatment Groups	Group 1: optimal standard of care (control group) Group 2: high dose vitamin D3 supplementation added on top of optimal standard of care. Patients will be randomised to treatment or control group in a 1:1 ratio.

Study Flow and Assessments	
The study is divided into three parts:
 

• Screening phase: Patients are recruited at the Departments of Dermatology, Oncosurgery or Medical Oncology at the University Hospitals Leuven (Belgium), and other European academic sites. If all eligibility criteria are met, patients are then randomized to the treatment or control group. Randomisation is completed via IVRS. Patients are randomized as they come.

• Treatment phase: Vitamin D3 supplementation is given to the patients assigned to the treatment group and placebo to the control group in a double blind manner. Every participant is expected to take in the study drug orally once each month. Study duration is a maximum of 3.5 years or until relapse occurs.

• Follow-up phase: Every participant will be followed up every 3 months up to the final study visit. Endpoints will be reported as occurring throughout the follow up. Defined endpoints are adjudicated by an independent Clinical Endpoint Committee (CEC) blinded to the patient treatment allocation. This ensures a consistent and unbiased adjudication of events.

 
Study data are reviewed by a Data and Safety Monitoring Board (DSMB) that reviews key safety data on an ongoing basis.

-----------------------------------	--

Therapy	Ampoules of 100 000 IE cholecalciferol (vitamin D3) are prepared by the pharmacist and will be taken orally at a monthly basis. Duration of the treatment: till the end of the study (max 3.5 years) or until relapse. Placebo capsules, consisting of oil preparation will be prepared in the same way. All patients are treated with optimal standard cutaneous melanoma follow-up.
Population	Adult male or female patients with histologically diagnosed stage IB to III cutaneous melanoma are eligible for the trial.
Inclusion Criteria	

1. Older than 18 years and younger than 80 years of age.

2. Histologically proven malignant melanoma, stage IB to III Not participating in other clinical trial.

3. The only treatment for melanoma is surgical treatment.

4. Complete resection of melanoma.

5. Single primary invasive cutaneous melanoma (inclusion within 1 year after diagnosis).

6. Signed ethical committee approved informed consent

7. Serum phosphate and calcium at the entry of the study within normal range of the laboratory reference

Exclusion Criteria	

1. Pregnant/lactating women or planning on becoming pregnant during the study

2. Known hypersensitivity to vitamin D or its components.

3. Pre-existing renal stone disease or chronic renal disease with eGRF < 30 mL/min/1.73 m^2 or renal dialysis.

4. Liver failure or chronic liver disease with liver enzyme > 2 fold ULN (=upper limit of normal)

5. History of parathyroid disease or granulomatous disease (TBC and sarcoidosis)

6. History of malabsorption syndrome or any medical condition that might interfere with vitamin D absorption.

7. History of other malignancy within the last 5 years except for carcinoma in situ of the cervix or basal cell carcinoma or squamous cell carcinoma of the skin or in situ malignant melanoma.

8. Chronic alcohol abuse.

9. Medical or logistic problems likely to preclude completion of the study.

Study duration	Patients are enrolled during a recruitment phase of three years maximum. Study duration for one patient is maximum 3.5 years or until relapse occurs. The DSMB may terminate the study earlier based on safety concerns.

Criteria for Evaluation	Primary efficacy endpoint: 1. Relapse free survival  Secondary efficacy endpoints: 1. Melanoma subtype, as assessed clinically and histologically 2. Melanoma site, as clinically recorded 3. 25(OH)D3 serum levels at diagnosis and at 6 months intervals 4. Stage of melanoma patient at diagnosis according to the 2009 AJCC Melanoma staging and classification  Safety endpoints: • Incidence and severity of adverse events
Sample size	Approximately 500 patients.
Version and date of final protocol	First version, 10-10-2012
Version and date of protocol amendments	Second version, 22-03-2013 Third version, 20-08-2013 Fourth version, 25-11-2015 Fifth version, 27-09-2017 Sixth version, 20-02-2018 Seventh version, 19-03-2019 Eight version, 05-01-2021

Statistical methods	The analysis of efficacy and safety will be performed for an intention-to-treat (ITT) population, defined as all randomized patients. No interim analysis for efficacy is foreseen. .
----------------------------	--

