#### **Safety endpoints:**

[figure not shown]
- Incidence and severity of adverse events

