#### **4.3.8. Study duration for study patients**

Each enrolled patient will remain in the study throughout the entire study duration, with a maximum study follow-up of 3.5 years for each patient. A study patient's participation may be terminated early because of relapse/progression which is the main study end point or due to a reasonable cause, such as the investigator's medical decision. At any time, the patient has the right to withdraw consent without a negative impact on her/his medical treatment.

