### 6.3. Collection period

In this study, the collection period for serious adverse events starts at randomisation and ends when the patient completes the study or at premature termination.

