## **7. STATISTICAL METHODS**

### **7.1. Sample Size**

Approximately 500 patients for the treatment group and for the control group are required. Assuming similar times to relapse as retrospectively observed at the University hospital Leuven, 3 year of recruitment and a total study duration of 3.5 years, 500 patients will have 90% power to detect a hazard ratio of 0.40 in favour of the vitamin D supplemented arm by means of Cox proportional hazards model stratified for time since diagnosis (3 strata: 0, 6 or 12 months ago). The hazard ratio of 0.40 is in correspondence with the intermediate effect size that was reported by Newton-Bishop et al (2009) and a potential increase in VD serum levels of 70 nmol/L which is 80% of the observed effect in a study with CPOD patients (Lehouck et al, 2012). It is anticipated that no patient will be lost for follow-up.

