### **7.2. Statistical Methods**

The primary analysis is an intent-to treat analysis of all randomised patients. Patients will be analysed according to the treatment group to which they were randomised, irrespective of which study drug was given or if any study drug was received. Additional populations like a per protocol population may be defined in the statistical analysis plan

The difference in relapse-free survival will be compared between the two treatment groups by means of a Cox proportional hazards model stratified for time since diagnosis (3 strata: 0, 6 or 12 months ago). It will be verified whether the treatment effect is stratum dependent. If so, the strata will be analysed separately. Furthermore, using a Cox proportional hazards model it will be investigated whether the potential treatment effect is different for VDR immunoreactivity and genetic variability in the Vitamin D pathway. A correction for other baseline covariates like gender, age and

baseline Vitamin D level will be performed as sensitivity analyses. No interim analysis for efficacy is foreseen. Potential subgroups analysis like for instance calcium serum levels will be defined in the statistical analysis plan

The evolution in 25(OH)D3 levels in function of genetic variability in the Vitamin D pathway will be analysed by a linear mixed model. Sensitivity analyses will include patient's compliance, seasonal effects and patient's baseline characteristics like age and gender.

In order to examine the effect of the actual 25(OH)D3 levels rather than just supplementation, the evolution of 25(OH)D3 levels and relapse-free survival will be jointly modelled.

The potential correlation between VDR immunoreactivity and stage at diagnosis will be assessed by means of a Kruskal Wallice test.

The potential correlation between vitamin D levels at diagnosis with melanoma site and melanoma subtype will be assessed by means of an analysis of variance. This analysis can only be performed for newly diagnosed patients because vitamin D levels at diagnosis will not be available for patients who had their diagnosis 6 or 12 months ago.

Full details of the statistical analyses will be described in a statistical analysis plan which will be finalized before database lock.

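### Safety is assigned to all randomised patients, with no dosed safety set and no adjustment for observation time, although observation can end at relapse

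*Combined protocol and SAP*

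**What the plan says.** The synopsis, under Statistical methods, puts efficacy and safety in one population: "The analysis of efficacy and safety will be performed for an intention-to-treat (ITT) population, defined as all randomized patients". It is the only rule given for the safety analysis.

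Section 7.2 describes the primary analysis as intention-to-treat, "irrespective of which study drug was given or if any study drug was received". It gives no method for adverse events. On other analysis sets it says only: "Additional populations like a per protocol population may be defined in the statistical analysis plan". It defers full details to an SAP, to be finalised before database lock, that is not among the documents.

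The safety endpoint is "Incidence and severity of adverse events" (synopsis and section 2), with no denominator.

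The time during which events can be seen depends on relapse:
- Synopsis, Study duration: "Study duration for one patient is maximum 3.5 years or until relapse occurs". The Therapy entry ends treatment at the same point.
- Section 4.3.8: "participation may be terminated early because of relapse/progression which is the main study end point".
- Section 6.3: "the collection period for serious adverse events starts at randomisation and ends when the patient completes the study or at premature termination".
- Table 1 schedules the final collection of adverse events at study end or at progression/relapse.

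**The concern.** ITT protects the efficacy comparison, but for harm it errs in the unsafe direction. A patient who never took an ampoule stays in the denominator, and an event in a patient given the wrong product counts in the assigned arm. Both pull a real difference towards zero.

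The second problem is observation time. If relapse closes the window for adverse events, the arm with fewer relapses is watched longer and collects more events even when the drug causes none. If vitamin D raised the relapse rate, its window would be shorter and toxicity would be under-counted. Section 4.3.7 asks the DSMB to exclude exactly that increase in relapse, so the masking would occur in the scenario where a clear safety picture matters most.

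**Working it through.** **Inputs.** From section 7.1: "500 patients will have 90% power to detect a hazard ratio of 0.40 in favour" of vitamin D, 3 years of recruitment, 3.5 years in total, no loss to follow-up. From section 3.1 and the synopsis: 500 patients, 1:1, so 250 per arm. Not given: alpha, number of events and control relapse rate. Assumed: two-sided alpha 0.05, exponential times to relapse, uniform accrual, observation ending at relapse.

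**The plan's own figure.** The 90% power cannot be confirmed without the control rate, but it can be inverted. Events needed (Schoenfeld):

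d = 4(1.960 + 1.282)² / (ln 0.40)² = 42.03 / 0.8396 = 50.06.

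With follow-up uniform from 0.5 to 3.5 years, the probability of relapse at hazard h is

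P(h) = 1 − [exp(−0.5h) − exp(−3.5h)] / (3h).

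Solving 250·P(h) + 250·P(0.40h) = 50.06 gives h = 0.0770 per year in controls (3-year relapse about 21%): 35.2 + 14.9 events.

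**Mean observation time** is P(h)/h.
- Control: 0.1408 / 0.0770 = 1.83 years (457 patient-years).
- Vitamin D at HR 0.40: 0.0594 / 0.0308 = 1.93 years (482 patient-years).
- Ratio: 1.055.

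With the control hazard held at 0.0770:

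| HR | Vitamin D, mean years | Ratio to control |
|---|---|---|
| 0.40 | 1.929 | 1.055 |
| 0.70 | 1.878 | 1.027 |
| 0.80 | 1.861 | 1.018 |
| 1.00 | 1.829 | 1.000 |
| 1.50 | 1.751 | 0.958 |

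**A full 3.5 years for every patient.** Here P(h) = 1 − exp(−3.5h). Re-solving for 50.06 events gives h = 0.0435, mean times of 3.25 and 3.40 years, and a ratio of 1.046.

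**Range for the unstated control rate.** At HR 0.40, assumed 3-year control relapse of 10% / 30% / 50% gives ratios of 1.025 / 1.084 / 1.162 with staggered accrual and 1.037 / 1.126 / 1.246 with a fixed 3.5 years.

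**Effect on a crude proportion with no true drug effect** (HR 0.40, staggered accrual). For an adverse-event hazard m equal in both arms, the proportion is [m/(m+h)]·P(m+h).
- m = 0.1 per year: 16.4% control, 17.2% vitamin D (ratio 1.05).
- m = 0.3 per year: 40.1% control, 41.9% vitamin D (ratio 1.05).

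With 250 per arm these gaps are about 0.25 and 0.42 standard errors. A rate per patient-year or a time-to-first-event hazard ratio would be 1.00.

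**Dilution (illustration only).** The documents give neither event risks nor shares of patients undosed or mis-dosed. Assume true risks of 10% and 5%, a risk ratio of 2.00.
- A share q of the vitamin D arm never dosed, at the 5% risk: [(1−q)·10 + q·5]/5 = 1.99, 1.95, 1.90 for q = 1%, 5%, 10%.
- A share s swapped in both arms: [(1−s)·10 + s·5]/[(1−s)·5 + s·10] = 1.97, 1.86 for s = 1%, 5%.

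**The case against.** The defence has real force. Incidence may mean a proportion or a rate, section 7.2 prescribes neither, and section 4.3.6 even speaks of an infection rate. A later SAP could add a safety set and a denominator. The imbalance is a few per cent, needs a large treatment effect to reach 5%, and is well inside sampling error for a single event type. If vitamin D works, dilution and longer observation pull in opposite directions. Ampoules are numbered to the randomisation schedule (section 5.1.5), so frequent mis-dosing is not to be expected. Section 4.3.8 says only that participation may end at relapse.

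All of this limits the size of the point, and none of it removes the point. The synopsis does name a population for safety, so this is a stated rule as well as a gap. The only extra population that section 7.2 offers as an example is per protocol, which is not a safety set. Two errors of unknown size that may partly cancel are no substitute for a defined measure.

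Nor is relapse the only way out. Section 6.1.2 also ends the study for confirmed hypercalcaemia and for 25(OH)D3 below 10 ng/ml at 6 months or later. Both could differ by arm, possibly in opposite directions, so the net imbalance cannot be signed from relapse alone. That is a reason to report observation time by arm.

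**Conclusion.** The point stands at modest size. Safety is assigned to all randomised patients with no dosed set and no exposure adjustment, while observation can end at the primary outcome. If adverse events are shown as proportions or counts, vitamin D patients are observed about 5% longer at HR 0.40, 2-3% longer at HR 0.7-0.8, equally long at HR 1 and about 4% less at HR 1.5. This rests on two-sided alpha 0.05, exponential relapse, 250 per arm and observation stopping at relapse. If section 7.1 is read as 500 per arm, the HR 0.40 ratio (on 51 events) falls to 1.027. The dilution has the stated direction but no documented magnitude.

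Four stronger readings are tempting and not supported:
- That the plan commits to a crude proportion. It leaves the measure unspecified.
- That section 7.2 expressly orders safety to be counted whatever drug was received. That sentence concerns the primary analysis; for safety, as-randomised counting follows only from the ITT label in the synopsis.
- That observation would be 8% longer. This pairs the 0.0770 hazard with a full 3.5 years per patient (3.07 against 3.32 years, ratio 1.081), a combination that yields about 85 events where the stated power implies about 50.
- That the product taken can be read directly from the records. Section 5.1.5 registers how many ampoules were taken and when, not clearly which ones. Section 6.1.2 also allows extra D-Cure on serum level without naming an arm, so exposure to vitamin D is not simply the assigned arm.

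**What to change.** In the synopsis, section 7.2 and the SAP:
1. Keep ITT (all randomised patients) for efficacy.
2. Define the safety set as all patients who took at least one ampoule, analysed by study product received: the assigned arm unless dispensing records show otherwise.
3. Record extra D-Cure given under section 6.1.2 and describe it by arm as concomitant exposure.
4. Report adverse events per patient-year and as time to first event, with observation ending when adverse-event collection closes for that patient.
5. Tabulate observation time and reasons for ending it (relapse, laboratory criteria, withdrawal, study end) by arm.

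The cost is wording and a little more analysis. Intake counts and dates are already registered; whether dispensing records can confirm the product for each patient should be checked before rule 2 is fixed. Never-dosed patients leave the safety denominator, and an as-randomised table can be kept as a sensitivity analysis. Because section 7.2 leaves the SAP open until database lock, the change can still be made there, preferably before anyone outside the DSMB sees data by arm.

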## List of Abbreviations

7-DHC	7 Dehydrocholesterol
AE	adverse event
AJCC	American Joint Committee of Cancer
ALM	Acrolentiginous malignant melanoma
BCC	Basal cell carcinoma

CE	clinical event
CEC	clinical event committee
CMM	Cutaneous malignant melanoma
DSMB	data and safety monitoring board
eCRF	electronic case report form
GCP	good clinical practice
GMP	good manufacturing practice
IMP	investigational medicinal product
IVRS	interactive voice response system
LMM	Lentigo Malignant Melanoma
NMM	nodular malignant melanoma
SAE	serious adverse event
SCC	Squamous cell carcinoma
SSMM	superficial spreading malignant melanoma
SUSAR	suspected unexpected serious adverse reaction
VDR	Vitamin D Receptor

## 1. INTRODUCTION

### 1.1. Background

Cutaneous malignant melanoma (CMM) is the most common lethal skin disease, affecting mainly Caucasians worldwide and currently in Flanders the 10th most frequent tumor in males and 5th most frequent tumor in females (Belgian Cancer Registry 2008). Although CMM only accounts for 4 % of all malignant tumors of the skin, it is responsible for 80% of the skin cancer related deaths (Miller, 2006; Jemal, 2008). Incidence rates of this disease have been escalating in the last decades and it is forecasted that the incidence will further exacerbate the coming years (Garbe, 2009). In Belgium, a steady rise in the incidence of cutaneous melanoma has been reported as well (Belgian Cancer Registry, 2008). CMM arises from transformed melanocytes in the skin. These melanocytes are situated in the basal layer of the epidermis. Melanomagenesis implicates a stepwise transformation of melanocytes to melanoma, all or not with intermediate steps comprising ordinary and dysplastic naevi, and subsequent superficial and deep invasion, and metastasis (Miller, 2006). Several risk factors have been linked to the development of malignant melanoma. The strongest risk factors for melanoma are a family history of melanoma (two or more cases of melanoma in first degree relatives), multiple benign (more than 100) or atypical naevi, and a previous melanoma. Immunosuppression, low phototype (characterized by having a fair skin, poor ability to tan or freckled complexion with or without red hair), and exposure to ultraviolet light (especially short bursts of acute exposure in childhood and severe sunburn) are additional risk factors (Bataille, 2008). Each of these risk factors corresponds to a genetic predisposition or an environmental stressor, which contributes to the genesis of melanoma. At least some of these factors are understood to various degrees at the molecular level. For example 25 to 40 percent of the members of melanoma-prone families have mutations in cyclin-dependent kinase inhibitor 2A (CDKN2A). Polymorphisms in the melanocortin 1 receptor (MC1R) have been linked to fair skin and red hair and have been associated with increased risk of melanoma (Miller 2006). Single nucleotide polymorphisms at 9p21 and 22q13 involved in cutaneous nevi development (Falchi, 2009) have also been associated with increased melanoma risk (Bishop 2009).

The most important clinicopathological subtypes of melanoma are superficial spreading malignant melanoma (SSMM), nodular malignant melanoma (NMM), lentigo malignant melanoma (LMM), and acrolentiginous malignant melanoma (ALMM). SSMM is the most frequent subtype within the Caucasian population. Diagnostic signs are progressive asymmetrical enlargement of a pigment lesion which also demonstrates irregularity in colour and irregularity in shape.

NMM are less frequent, occur mostly in males and are the most aggressive form, since they show a vertical growth phase from the beginning. They present themselves as rapid growing black often ulcerated tumors. LMM arises in a long standing pigmented precursor lesion and is located on chronic photodamaged skin. ALMM appear on palms and soles initially as flat pigmented lesions resembling moles, which start to increase in size and ultimately develop irregular areas of pigmentation. Subungual melanomas are most often located on the thumb nail of the great toe and present themselves as a narrow pigmented band, which slowly widens and ultimately produces a subungual mass. Different risk factors are associated with different subtypes of CMM and different locations of malignant melanoma: while chronic photodamage preferentially associates with LMM and malignant melanoma on head and neck region, a high count of naevi preferentially associates with malignant melanoma on the trunk, indicating that different pathways may lead to the development of malignant melanoma, i.e. a pathway through chronic sun exposure, and a melanomagenetic pathway (Whiteman, 2003). Different subtypes of malignant melanomas show also a significant genetic heterogeneity: CMM arising in sites intermittently exposed to the sun harbor BRAF and/or N-ras mutations more frequently; while malignant melanomas on chronically sun exposed skin (LMM) and ALM show more frequent c-Kit mutations (Curtin 2006). While cutaneous malignant melanoma, when diagnosed and treated in an early stage (pure radial or early invasive growth phase) has a very good prognosis and can still be treated in a curative way via surgery, metastatic melanoma decreases the chances of survival markedly, because of the inherent resistance of the melanoma cells to classical cytotoxic chemotherapy. The most important predictor of progression of malignant melanoma and survival is Breslow thickness of the primary tumor at diagnosis. Breslow thickness is a histological characteristic of the tumor and refers to the thickness of the tumor, measured as the distance between the granular layer of the epidermis and the deepest tumor cell in millimetres. According to the recent final version of the 2009 American Joint Committee of Cancer (AJCC) melanoma staging and classification, primary tumor ulceration and primary tumor mitotic rate are considered as independent prognostic factors for survival and have been included in tumor staging (Balch 2009). For instance, patients with a melanoma equal or less than 1 mm thickness, without ulceration or mitosis and without nodal or distant metastasis (T1aN0M0, stage IA) have a very good prognosis, reflected by a five and ten year survival of respectively 97 and 93%, whereas patients with an ulcerated melanoma of over 4 mm thickness, but without nodal or distant metastasis at diagnosis (T4bN0M0) have a 5 and 10 year survival of 53% and 39% respectively. Once distant metastasis occurs, the prognosis is bad, i.e. a patient with distant metastatic melanoma to the viscera (stage IV, M1c) has a 1 year survival of 33% (Balch 2009). Other known predictive prognostic factors are presence and distribution of tumor infiltrating lymphocytes, tumor site, sex, and social deprivation. (Balch, 2009; Newton Bishop 2009).
